Title: **Group ("Project Life Force") vs. Individual Suicide Safety Planning RCT**

NCT Number: **NCT03653637**

Date: **05/12/2025**

Primary Statistical Analysis Plan

The primary outcome of suicidal behavior will be analyzed using a Cox Proportional Hazard Regression, with treatment condition (PLF+TAU vs. TAU) and baseline suicidal behavior level as predictors, and incidence and time to the first suicidal behavior during the study course as the outcome variables. The model will adjust for treatment site. Kaplan-Meier estimates of the cumulative hazard function for both groups will be graphed and the proportionality assumption checked. If the hazard functions are not proportional, the non-parametric log-rank test will be used instead, with treatment condition as predictor, and we will use a sensitivity analysis to test the effect of baseline suicidal behavior severity by splitting the treatment conditions by the presence/absence suicidal behavior.

Most secondary and other outcomes (depression, hopelessness, thwarted belongingness, aggression dimensions, insomnia and suicide-related coping) will be analyzed in Linear Mixed Effects (LME) regression models. All LMEs will be adjusted for site and will include randomization condition, time, and a randomization by time interaction. The treatment effect of PLF+TAU vs TAU will be the treatment by time interaction. Time will be treated as a linear variable. Mixed-effect models can be fit to data with dropout or missing values as long as the data is missing at random, thus, attrition does not necessarily reduce the number of participants included in these analyses.

For the two outcomes (drug and alcohol use) that are only measured at the one-year follow-up (with retrospective questions about the past 12 months), we will compare between PLF+TAU and TAU with t-tests or Mann-Whitney U tests where appropriate.

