6. State inclusion criteria for enrollment in study:

Inclusion Criteria include: 1. Age 18 years or older, 2. Discharge from inpatient unit for suicidal ideation or attempts, or placement on the high-risk suicide list maintained by suicide prevention coordinators, or patient from outpatient service that meets criteria of 4 or 5 on CSSRS or attempt within the past year 3. Concurrence from the patient's mental health provider for the Veteran to participate in the study and the provider is willing to work with the research team.

7. State exclusion criteria for enrollment in study:

Exclusion Criteria include: 1. Unable to provide informed consent or complete study requirements, 2. Unable to speak English, 3. Cognitive difficulties that impair consent Capacity, 4. Unable or unwilling to provide at least one verifiable contact for emergency or tracking purposes, 5. Unable to attend outpatient group treatment program or tolerate group therapy format, 6. Active alcohol or opiate dependence requiring medically supervised withdrawal, 7. Schizophrenia diagnosis, 8. Participation in another intervention RCT.

8. Will vulnerable subjects be enrolled in this study?

YES	X	NO	
------------	----------	-----------	--

	YES	NO
Individuals with lack of decision-making mental capacity		X
Economically/socially disadvantaged persons	X	
Educationally disadvantaged persons	X	
Pregnant women, for minimal risk only		

Fetuses Requires Medical Center Director authorization. See IRB SOP.

Children Requires Medical Center Director authorization. See IRB SOP.

Prisoners Requires CRADO authorization. See IRB SOP.

If Yes for any answer, provide a means by which vulnerability is determined: **Vulnerability will be determined through gathering basic demographic data of each participant. James J. Peters VA Medical has a population of veterans who are economically, socially, and educationally disadvantaged; thus, the PI anticipates recruiting from vulnerable populations.**

9. Are prospective subjects likely to feel vulnerable to coercion or undue influence to enter the study?

YES		NO	X
-----	--	----	---

a. Are there any payments to subjects?

YES	X	NO	
-----	---	----	--

b. If No, proceed to question 9.c.

How much are the payments? **\$50-\$75**

Provide a schedule (timing) of payments. **Baseline, post intervention, 3 months post completion of intervention, 6 months post completion of intervention**

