b. Provide a detailed **list of tests and procedures** that will be performed for research purposes (e.g., blood tests, urine tests, cultures, interviews, questionnaires, surgical procedures, cardiac catheterization, pulmonary function tests, X-rays, scans, etc) during the course of the study. **List must indicate tests and procedures only for subjects who sign a VA consent form, regardless of where tests and procedures take place:**

Test /Procedure:	Where:	Performed by Whom: (Insert Name or TBD if not yet known)	When:	# of times:
Columbia Suicide Severity Rating Scale (CSSRS)– current & since last visit version	Research office	[name], [name]	0, 3, 6,12, weekly for PLF group participants	4
Access to Lethal Means	Research office	[name], [name]	0, 3, 6,12	4
Beck Depression Scale	Research office	[name], [name]	0, 3, 6,12	4
Beck Hopelessness Scale	Research office	[name], [name]	0, 3, 6,12	4
Self-report log based on the Modified Cornell Services Index (MCSI)	Research office	[name], [name]	0, 3, 6,12	4
Brief Survey of Safety Plan Utilization (BSSPU)	Research office	[name], [name]	0, 3, 6,12	4
Suicide-Related Coping Measure (SRCM)	Research office	[name], [name]	0, 3, 6,12	4
Group Psychotherapy Process Measure*	Research office	[name]	1,5,10 (weeks)	3

PLF treatment arm only		[name]		
Buss-Perry Aggression Questionnaire	Research office	[name], [name]	0, 3, 6,12	4
Reasons for Living	Research office	[name], [name]	0, 3, 6,12	4
Attitudes Towards Seeking Professional Psychological Help	Research office	[name], [name]	0, 3, 6,12	4
Insomnia Severity Index	Research office	[name], [name]	0, 3, 6,12	4
Beck Lethality Scale	Research office	[name], [name]	0, 3, 6,12	4
The Self-Injurious Thoughts and Behaviors Interview	Research office	[name], [name]	0, 3, 6,12	4
Suicide Intent Scale	Research office	[name], [name]	0, 3, 6,12	4
Beck Scale for Suicidal Ideation	Research office	[name], [name]	0, 3, 6,12	4
Barratt Impulsiveness Scale	Research office	[name], [name]	0, 3, 6,12	4

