For the survival analysis comparing the PLF and TAU treatment conditions, we assumed a 20% dropout in both groups based on previous safety planning data to date using SAFE-VET, exponential hazard functions, and considered four scenarios of suicide behavior reduction of PLF over TAU. We assumed a base rate of 49% for SB in the TAU group based on published data from ED-SAFE. The sample sizes needed for 80% power were calculated using the “Proc Power” procedure from SAS software © 2002- 2012. In the absence of pilot data, we used a published formula for the Variance Inflation Factor from the weighted log-rank test, to adjust the required sample size for within-group, and within-clinician, dependence. We assumed m=5 subjects per group or clinician, and an ICC for suicidal behavior within the group of r=0.01 based on literature. While power analyses were calculated for several reduction rates, we selected the 35% reduction rate as the most reasonable estimation for the reasons outlined below. The composite suicide behavior outcome has minimal data outside of ED-SAFE’s reduction of 18% in non-veterans recruited from an emergency room. Stanley and Brown’s SAFEVET data on Veterans presenting to an ED, reported a 45% reduction in suicide attempts (however the composite definition of suicidal behavior was not used). Moreover we anticipate PLF to have increased potency over SAFEVET due to the group setting and greater number of in-person sessions. Balancing the enhanced potency of the PLF intervention with the new composite definition of SB, the 35% reduction scenario is reasonable. Therefore, we expect the reduction to be above the minimum values indicated, and are confident that N=145 will provide ample power for this aim. Then, the research team included an additionally 35 to be consented who would likely not screen into the study or meet inclusion/exclusion criteria.

18. Community-based Participatory Research

Is this research based on Community-based participation?

YES		NO	X
------------	--	-----------	----------

If Yes, answer questions (a-h). If No, proceed to Question 19.

a. Describe the community that will be involved in this research:

b. What is the role of the community in this research?

c. Does this research include a community organization that is engaged in research?

YES		NO	
------------	--	-----------	--

If Yes, does that organization have a Federal Wide Assurance (FWA)?

YES		NO	
------------	--	-----------	--

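### The primary Cox model leaves out baseline suicidal ideation severity, which is scheduled at time 0 in both arms; the analysis stays valid, but it may give up some power.

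*SAP*

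**What the plan says.** The SAP (Primary Statistical Analysis Plan) analyses time to first suicidal behavior by Cox regression "with treatment condition (PLF+TAU vs. TAU) and baseline suicidal behavior level as predictors". It adds: "The model will adjust for treatment site". No ideation score is named. The fallback for non-proportional hazards is a log-rank test by arm, with a sensitivity split on whether suicidal behavior was present at baseline; ideation plays no part there either.

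The protocol's table of tests (section 13.b) schedules two instruments that bear on baseline ideation, the "Beck Scale for Suicidal Ideation" and the "Columbia Suicide Severity Rating Scale (CSSRS)– current & since last visit version". Both are listed at 0, 3, 6 and 12, and neither is confined to one arm at time 0. Section 13 places the baseline measures before randomisation.

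The inclusion criteria (section 6) offer alternative routes in. Inpatients qualify on leaving hospital after an admission for either ideation or an attempt, and Veterans whom the coordinators have listed as high risk also qualify. The remaining route is: "patient from outpatient service that meets criteria of 4 or 5 on CSSRS or attempt within the past year".

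Two other passages of section 17.a touch on covariates. One promises adjustment for covariates of interest and imbalanced prognostic factors, but it concerns the linear mixed models and names none. The other, on missing data, mentions baseline scores as predictors in both survival and mixed models, again without naming any. Neither puts ideation into the Cox model.

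**The concern.** The model's only patient-level baseline covariate is past suicidal behavior. Someone can enter on ideation without a recent attempt, and the trial plans to measure ideation severity before randomisation. If that severity predicts time to first suicidal behavior beyond what past behavior already tells, leaving it out of a Cox model moves the estimated hazard ratio toward 1 and lowers power, even under perfect randomisation. Few first events are expected, so precision available from data already scheduled is worth having.

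**Working it through.** **Inputs from the documents.** Section 17.b of the protocol: "We assumed a base rate of 49% for SB in the TAU group based on published data from ED-SAFE"; a 35% reduction; 20% dropout in each arm; exponential hazards; m=5 and ICC=0.01; 80% power; N=145. Section 13: half randomised to PLF. Section 4.f: 12 to 14 months of participation.

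**Assumptions.** Two-sided alpha of 0.05 (not stated); 49% as a 12-month risk; variance inflation 1 + (5 − 1) × 0.01 = 1.04 (the published formula is not given); the 35% as a cut in the proportion, so 0.49 × 0.65 = 0.3185.

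**Step 1: the plan's own figure.**
- Hazard ratio: ln(1 − 0.3185)/ln(1 − 0.49) = 0.569.
- Events for 80% power (Schoenfeld): 4 × (1.960 + 0.842)² / (ln 0.569)² gives 100 after rounding up.
- Chance of an observed event, with hazard λ and dropout hazard μ = −ln(0.8) = 0.223: λ/(λ+μ) × (1 − e^−(λ+μ)). For TAU, λ = 0.673 gives 0.445. For PLF, λ = 0.383 gives 0.288. The mean is 0.366.
- Total N: 100/0.366 × 1.04 ≈ 284, or 142 per arm.

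So 145 does not reproduce as a total, though 142 per arm is close to it. Section 17.b adds 35 to 145 to reach the 180 to be consented, so the text treats 145 as the total. I therefore checked both N=145 and N=290 (145 per arm).

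**Step 2: events and power at N=145.** Events: 145 × 0.366 = 53.1. After inflation, 53.1/1.04 = 51.0. Power: Φ(√51.0/2 × 0.563 − 1.96) = Φ(0.05) ≈ 52%.

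**Step 3: what the ideation score would add.** The documents give no prognostic strength for ideation, so a range was assumed and simulated. Settings were exponential survival, marginal 12-month risks held at 49% and 31.85%, 20% dropout, a binary baseline-behavior covariate (hazard ratio 1.5 assumed), three sites, and a standardised ideation score. Its correlation with the factor underlying baseline behavior was 0, 0.3 or 0.6 (0.3 only at a hazard ratio of 1.0). There were 3,000 trials per setting at N=145 and 1,500 at N=290, without clustering. The Wald test for arm was compared with and without the score. Monte Carlo error on one power figure at N=145 is about 1 point.

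| Assumed HR per SD of ideation | N=145, SAP model | N=145, plus score | Gain at N=145 (points) | Gain at N=290 (points) |
|---|---|---|---|---|
| 1.0 | 53.1% | 53.0% | −0.1 | −0.1 |
| 1.25 | 51.7–56.3% | 51.7–56.2% | 0 to 0.7 | 0.5 to 1.9 |
| 1.5 | 53.2–55.4% | 56.4–58.0% | 2.6 to 3.2 | 1.5 to 2.8 |
| 2.0 | 53.0–57.4% | 62.5–66.1% | 8.1 to 9.5 | 4.5 to 6.1 |

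A separate simulation of 3,000 trials per setting at N=145, with no site term, gave 52.5% to 52.6%, 53.7% to 54.8%, 53.5% to 57.4% and 52.4% to 62.4%. Those are gains of 0.1, 1.1, 3.9 and 10.0 points. Together the two sets give about 0, 0 to 1, 3 to 4 and 8 to 10 points.

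At N=290 the SAP model alone has 81.5% to 88.3% power, so there is less to gain.

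**Step 4: price of the extra term.** If the four sites named in section 17.a are fixed effects, the SAP model has 1 + 1 + 3 = 5 parameters. Events per parameter go from 53.1/5 = 10.6 to 53.1/6 = 8.9. The first row of the table shows no material loss of power when the score is useless.

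**The case against.** The strongest reply is that nothing is wrong. The SAP already adjusts for the baseline form of the outcome and for site, and omitting a further covariate leaves the randomised test unbiased. The shift of the hazard ratio toward 1 reflects a less conditional estimand. That stands: a reader who infers an error or a biased primary test goes further than the documents allow.

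It also stands that the loss is conditional. Only what ideation adds beyond baseline behavior counts. At a hazard ratio of 1.25 per SD the gain is indistinguishable from nothing, and only the top assumption gives a sizeable one. If the SAP's behavior covariate is graded rather than binary, less may be left to gain.

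The entry criteria do not settle the matter. Selecting on ideation could narrow its spread among those enrolled. Equally, the routes are alternatives, and some need no ideation level. One might infer that past behavior is uninformative for many participants, but no document gives the share entering on ideation alone, and section 3.b describes a population with a history of attempts as well as ideation.

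Nor may one infer that every participant will have a score: section 13.b shows scheduling, not completeness. Other baseline measures (hopelessness, depression, the CSSRS) could also be candidates, and the documents do not rank them. The case for this score is that it measures ideation directly and that reducing ideation is the purpose stated in section B.2.

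These points reduce the concern without removing it, because adding the term costs almost nothing even when it is useless.

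**Conclusion.** The point holds as a low-cost improvement, not as a correction of an error. The primary Cox model is valid as written but possibly inefficient. The gains in Step 3 rest on assumed prognostic hazard ratios from 1.0 to 2.0 per SD, assumed correlations with baseline behavior, an assumed two-sided 0.05 test, and a 35% cut read as a change in proportion. Reading it as a hazard ratio of 0.65 lowers power at N=145 to 35–38%; the gain under that reading was not simulated.

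A reader might infer that adjustment would rescue the trial's power. It would not: the highest figure at N=145 is about 66%, against the 80% planned. The shortfall between 145 and the plan's own inputs is a separate and larger matter. The gain is also available only if the Cox model is kept, since the log-rank fallback carries no covariates.

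**What to change.** Add one sentence to the SAP: the primary Cox model will include the time-0 total of the "Beck Scale for Suicidal Ideation" as a continuous term, beside arm, baseline suicidal behavior level and site, with missing baseline scores imputed by a stated rule that takes no account of arm.

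The documents do not say whether outcomes by arm have been examined. If they have, keep the present model as primary and report the extended model as a sensitivity analysis, labelled as such.

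The cost is one degree of freedom and simple handling of missing baseline scores. No new data collection is needed.

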Title: Group ("Project Life Force") vs. Individual Suicide Safety Planning RCT

NCT Number: **NCT03653637**

Date Approved: **08/03/2024**

B. PROTOCOL SUMMARY

1. Provide a brief (200-250 word) summary of background information for physician/scientists. List total # of subjects approved for enrollment by the IRB.
List total number of subjects enrolled (Signed a consent form) over the life of this study. List total number of subjects enrolled(Signed a consent form) in the current approval period. List total number of subjects terminated from study (Lost to follow-up, terminated by PI, withdrew consent, etc.). List total number of subjects that have completed all study tasks/procedures and follow-up visits. List total number of subjects currently receiving study treatment or participating in study activities.:

At present, we are unaware of any empirically supported, manualized outpatient group treatments for suicidal individuals other than a published account of a 1-session inpatient safety planning group and description of an outpatient process oriented group of variable session length and duration. Dialectical Behavior Therapy (DBT) offers a group component in its comprehensive approach, but discussion of suicidal urges, thoughts and behaviors is discouraged in the group setting. The paucity of published literature on group approaches for suicidal individuals is surprising given the numerous advantages of group treatment that include: 1) diminishing social isolation and increasing social support, a protective factor against suicide; 2) it's cost effectiveness and maximizing staff time; 3) the peer movement among those who have experienced suicidal crises is strong and growing; and 4) Veterans and military service members are used to working with a team approach to problems.

PLF is one of the first outpatient manualized suicide prevention group intervention to date. The proposed study has direct VA and military relevance as psychotherapy groups are a standard treatment modality in both settings.

2. State the purpose of the study:

The study proposes to conduct a randomized clinical trial (RCT) of a group safety planning intervention, “PLF” versus individual safety planning in 180 suicidal Veterans. Compared with the comparison condition- individual safety planning, the current standard of care, designated as treatment as usual (TAU), the PLF group will show a decrease in suicidal ideation.

3. Background of Study Population - Clinical Information:

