As mentioned above, upon hearing the description of the study, the participant will be required to describe the procedures to the person obtaining consent, summarize what is expected of him or her and list two risks involved. This will ensure that participants understand the implications of their decision to participate and are able to make a well-informed decision and communicate this decision to the person obtaining consent. Consent will be obtained in a private setting by an investigator to minimize any power differential that the participant might feel. Participants unable to communicate with the investigator for any reason will not be included in the study. Only subjects having the capacity to give informed consent will be enrolled in the study. The recruitment process will not be coercive or unduly influencing, as participants enter the research study voluntarily and understand that they have the right to withdraw at any time. Subjects will be told that non-participation in the study will not affect any current treatments they are receiving at VA or elsewhere.

13. Summarize what actually will be done to the subjects during their participation in the study:

The subject will fill out the informed consent. They will then fill out a series of clinician interviews and self-report measures asking questions related to thoughts and feelings about suicide, general mental and physical health, and relationship with other. After these are completed half the group will be randomized to the PLF intervention arm in which Veterans will participate in the 10 weekly groups.

a. Provide a clear description of what is being done for research purposes and what is being done as part of "usual care":

For research purposes: Initial consult with research investigators and consenting, which will take approximately 30 – 45 minutes, completing assessments (1.5 hours) and answering interview-style questions pertaining to the research topic (30 minutes).

Subject matter of the interview includes: communication quality with others, overall life satisfaction, frequency of suicidal ideation or urges, and reasons for attempting suicide.

“Usual care”: Subjects will be able to continue all regular treatment outside of the study.

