All data will be de-identified before it is entered into a redcap database at the JJPVA, Philadelphia VA, Northport VA, and Central Texas VA over the intranet. All principal analyses will be conducted based on the intention-to-treat principle. Linear mixed models will be used to examine changes in primary and secondary outcomes for Veterans over time and to examine whether the effects of PLF and TAU on these outcomes vary with time adjusted for the time-dependent treatment, covariates of interest and imbalanced baseline prognostic factors, using data reduction methods as appropriate. *For the PLF subjects, individual's random effect will be nested within the group they are assigned to, while for TAU subjects, they will be nested within the clinician effect.* All data will be entered into an SPSS database at the JJPVA constructed by the data manager. Tenets of our data system include double data entry, range checks and exclusion of identifiers that can be directly traced to individuals. Preliminary analyses will include computing descriptive statistics and inspecting features and patterns of data to determine whether data transformations are needed. Quantitative measures will be graphed and their distribution inspected for any outlier value, which will be winsorized. All principal analyses will be conducted based on the intent-to-treat principle, that is, all Veterans with data will be included, regardless of the actual treatment received. For subjects who drop out during the study, their data up to that point will be used, but not carried forward to subsequent time points. We will also conduct an economic cost analysis of the Project Life Force intervention to compare cost effectiveness of telehealth groups versus the in-person groups pre-COVID. We will use an implementation science framework, The Consolidated Framework for Implementation Research, to determine barriers and facilitators of the telehealth-delivered PLF safety planning intervention. Development of the script and qualitative analysis will be conducted by [name]; a qualitative and implementation expert.

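### The protocol asks about group versus individual safety planning, but the SAP analyses PLF+TAU against TAU without saying what individual planning the PLF arm receives, and the SAP's models name no clustering term

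*SAP*

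**What the plan says.** **The question.** Both documents carry a title that sets group against individual safety planning. Protocol B.2 describes a randomized trial of PLF "versus individual safety planning in 180 suicidal Veterans" and continues: "Compared with the comparison condition- individual safety planning, the current standard of care, designated as treatment as usual (TAU), the PLF group will show" (the outcome named there is suicidal ideation). In that sentence TAU is the name for individual safety planning.

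**The analysed contrast.** The SAP's Cox model for suicidal behavior has "treatment condition (PLF+TAU vs. TAU) and baseline suicidal behavior level as predictors". For the mixed models it says "The treatment effect of PLF+TAU vs TAU will be the treatment by time interaction". The drug and alcohol comparisons at one year use the same two labels.

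**Care outside the study.** Protocol 13.a says under usual care: "Subjects will be able to continue all regular treatment outside of the study". It makes no exception for either arm. Inclusion criterion 3 (protocol section 6) requires, for every participant, "Concurrence from the patient's mental health provider for the Veteran to participate in the study".

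**Clustering.** Protocol 17.a, writing about linear mixed models, nests PLF participants within their therapy group, "while for TAU subjects, they will be nested within the clinician effect". Protocol 17.b inflates the survival sample size for dependence within groups and within clinicians, with m=5 and an ICC of 0.01. The SAP mentions adjustment for site in the Cox and mixed models and names no group or clinician term in any model.

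**The concern.** Put the protocol's definition of TAU into the SAP's contrast and the comparison becomes group plus individual planning against individual planning alone. A positive result would then support offering PLF on top of usual care. It would not show that the group format is better than individual planning, or that it can take its place.

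The difference has practical weight. Protocol B.1 promotes group treatment partly for its cost-effectiveness and its economy of staff time. A service that reads the title could take a positive result as grounds for substitution, which an add-on contrast does not test.

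The clustering gap is a second, smaller matter. People treated together in a therapy group may have correlated outcomes. A Cox or mixed model that ignores this gives standard errors that are too small when the correlation is positive. The sample size allowed for that dependence, but the SAP's models do not mention it.

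**Working it through.** **1. The contrast, side by side**

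- Protocol title and B.2: PLF versus individual planning, and individual planning is TAU.
- SAP, all three analysis types: PLF+TAU versus TAU.
- Protocol 13.a: regular treatment may continue, with no exception by arm. Criterion 3 gives every participant a cooperating provider. Both fit an add-on design.
- Protocol 17.a: PLF participants sit in a group only and TAU participants in a clinician only. This fits group in place of individual care.
- Protocol 3.e: traditional treatment is described more broadly, with behavioral psychotherapy and couple's therapy alongside general safety planning. TAU in the SAP could carry this wider meaning.

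The sections point in different directions, and none states what individual planning the PLF arm receives. If TAU means what B.2 says, the SAP's contrast is add-on. If TAU means general care kept by both arms, the safety-planning comparison could still be group versus individual, but the SAP's label would then not show it.

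**2. The size of the clustering terms**

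Inputs from protocol 17.b are m=5 and ICC=0.01. The protocol cites a published VIF formula but prints neither the formula nor its value, so there is no stated VIF to reproduce. I assume VIF = 1+(m−1)×ICC, equal arms (13 randomizes half to PLF), and, for a second level, the same m and ICC with clinicians not shared between arms.

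*One level in each arm, as in 17.a:* 1+4×0.01 = 1.04.

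*Clinician level added in PLF:* PLF arm 1+4×0.01+4×0.01 = 1.08; TAU arm 1.04; average (1.08+1.04)/2 = 1.06.

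Scaling the stated 145 by average design effect/1.04 gives the table below. ICCs of 0.05 and 0.10 are my assumptions, to show the range.

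| ICC | One level per arm | PLF arm, two levels | Average | N, one level | N, clinician added in PLF |
|---|---|---|---|---|---|
| 0.01 | 1.04 | 1.08 | 1.06 | 145 | 145×1.06/1.04 ≈ 148 |
| 0.05 | 1.20 | 1.40 | 1.30 | 145×1.20/1.04 ≈ 167 | 145×1.30/1.04 ≈ 181 |
| 0.10 | 1.40 | 1.80 | 1.60 | 145×1.40/1.04 ≈ 195 | 145×1.60/1.04 ≈ 223 |

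The added clinician level therefore costs about 2% at the stated ICC (1.06/1.04 = 1.019) and about 8% at 0.05 (1.30/1.20 = 1.083). Clinicians shared across arms would reduce both.

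*Group clustering in PLF only, against no clustering term:* the average design effect is (1.04+1)/2 = 1.02 at ICC 0.01, so intervals widen by √1.02 ≈ 1.01, or about 1%. At ICC 0.05 it is (1.20+1)/2 = 1.10, and √1.10 ≈ 1.05.

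The figure of 145 serves only as a base for these ratios. As a total it does not reproduce from the inputs in 17.b: I get about 284 with a 35% risk reduction from 49%, two-sided 0.05 (assumed), the Schoenfeld formula, exponential 20% dropout and VIF 1.04. That is a separate matter and leaves the ratios unchanged.

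**The case against.** The best defence is that the two labels may describe one design. If TAU in the SAP means the general care that everyone keeps, PLF+TAU against TAU could still compare group with individual safety planning. This stands as far as it goes: the documents do not prove an add-on design. But B.2 gives TAU the narrower meaning and the SAP gives it none, so the term still needs a definition.

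Three stronger readings are tempting, and the documents do not support them.

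- *The trial can only show an add-on effect.* This requires PLF participants to receive individual planning. 13.a only permits regular treatment to continue.
- *The SAP's contrast is what mixes format with contact.* PLF is 10 weekly sessions with weekly C-SSRS ratings (13.b), and no matching schedule is given for the comparator, so contact would probably differ head to head as well. 17.b attributes PLF's expected advantage to both the group setting and the number of sessions. Testing a package against standard care is a legitimate choice.
- *Clustering is misspecified by 4% to 20%.* VIFs of 1.04 and 1.20 measure one clustering level, which 17.b already allows for in principle. They do not measure the clinician term left out for PLF. Nor does the nesting sentence in 17.a describe the Cox model: it belongs to the protocol's mixed models.

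It is also fair to say that a clinician term needs identifiers that the documents do not describe for PLF participants, and that the provider in criterion 3 is not said to deliver TAU safety planning.

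**Conclusion.** The point holds as an inconsistency between the stated question and the analysed contrast. On B.2's definition of TAU the SAP estimates the effect of adding PLF, and the sections must be reconciled before results are worded. What cannot be concluded is which design was delivered.

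The clustering gap holds separately: the SAP states only site, although 17.a specifies nesting and 17.b sized for it. Its effect is small if the ICC of 0.01 is right: about 1% on interval width for group clustering in PLF, and about 2% on sample size for a further clinician level. These figures rest on the VIF formula, equal arms, m=5 and clinicians not shared. The stated ICC is for suicidal behavior, so it says nothing direct about the continuous outcomes in the mixed models.

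This should be corrected, mainly for what the trial may claim and only secondarily for its variance.

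**What to change.** 1. Define TAU once. State whether PLF participants also receive it and what individual safety planning it contains. Reconcile protocol B.2 and 13.a with the SAP, and use the same contrast in the purpose, the hypothesis and every SAP analysis.
2. If the arms are PLF+TAU and TAU, word the objective and conclusion as the effect of adding the PLF package to usual care, with no claim that the group format is superior to individual planning or can replace it. If PLF participants do not receive TAU as B.2 defines it, correct the SAP's arm labels.
3. Account for therapy-group clustering in the PLF arm: a shared frailty or cluster-robust variance in the Cox model, and a random group effect in the mixed models. State how the log-rank fallback will handle it. With about 145/2/5 ≈ 14 or 15 groups, a robust variance needs a small-sample correction.
4. Where clinician identifiers exist, add a usual-care clinician effect in both arms as a sensitivity analysis. In PLF this is crossed with therapy group and may be poorly estimated with clusters of 5, which is why it should not be primary.

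Items 1 and 2 cost only wording and, on the add-on reading, a narrower headline claim. Item 3 needs the group assignment of each PLF participant and gives slightly wider intervals. Item 4 may require clinician identifiers to be retrieved. No change of arms, outcomes or sample size is needed for this point.
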